Studies have shown that ACZ administered as a single 1000 mg IV bolus transiently enhances cerebral perfusion in healthy subjects (Sullivan et al., 1987; Vagal et al., 2009). Subjects challenged with IV ACZ had between a 30% to 60% increase in cerebral blood flow, as measured by Xenon-enhanced computed tomography scan, within 15 minutes of IV bolus (Sullivan et al., 1987). Another study using ultrasonography demonstrated that enhanced perfusion was sustained for at least 30 minutes with return to baseline measures within one hour (Hartkamp et al., 2012). This same dose and route of administration will be used in subjects with MS to determine the transient change to cerebral perfusion as quantified using MRI metrics as described in section 2.2.

Though ACZ IV transiently enhances cerebral perfusion, longer-term changes would be required to potentially impact lesion evolution. Daily or divided-daily infusions necessitate chronic IV access, pose increased risk to the patient and are impractical. Oral ACZ has been shown to also increase cerebral perfusion in patients with other neurologic disorders ("Acetazolamide Tablets | Drug Summary | PDR.net," n.d.) and might prove a practical and effective alternate chronic therapy for patients with MS.

ACZ has been used in daily divided doses up to a maximum of 4000 mg per day to treat pseudotumor cerebri (NORDIC Idiopathic Intracranial Hypertension Study Group Writing Committee et al., 2014). Participants in Stage 1b of this study will be given escalating divided doses of oral ACZ up to 1500 mg per day to determine both the magnitude of change to cerebral perfusion with each dose and define the optimum dose(s) for additional studies. In the final stages of this study (stage 2a and 2b), subjects will be treated with ACZ, as determined in stage 1b, for six consecutive months to determine if long-term change to cerebral perfusion alters the evolution of MS plaques into persistent black holes.

Rationale for Study Population

Multiple sclerosis affects predominantly persons between 15 and 55 years of age with females being nearly four-times as likely to be diagnosed with disease as males (Koch-Henriksen and Sørensen, 2010; Orton et al., 2006; Reingold, 2002). MS in the paediatric population is now better recognized and has been shown to differ from that in the adults in both clinical and radiologic presentation and evolution (Ghassemi et al., 2014; Renoux et al., 2007).

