This stage is designed to determine if daily oral ACZ is tolerated and if tachyphylaxis might occur with long-term use for the specific formulation of oral ACZ that we will utilize. Some authors have reported attenuation of the initial increases in CBF with sustained use or oral ACZ though still showing a persistent increase in cerebral perfusion of between 15% - 20%, when compared to pre-treatment levels (Friberg et al., 1990). In this stage, all subjects will receive baseline pCASL and DSC MRI and will start oral ACZ. Patients will continue on 1000 mg BID dose for 24 consecutive weeks and undergo repeat imaging at predetermined intervals. MRI scans and clinical evaluations will be obtained every 6 weeks with contrast-based scans repeated every 12 weeks. Contrast will be administered every 12 weeks to determine DSC measures of blood flow and whether new lesions have formed. As previously stated, DSC provides measurements of not only CBF but also blood volume (CBV) and transit time of blood (MTT). DSC techniques will provide information that cannot be obtained by using pCASL alone that might be important to determine how blood flow is altered with ACZ.

Stage 3 - Many factors contribute to the formation and evolution of lesions in MS (Cotton et al., 2003; Meier and Guttmann, 2006; Narayana et al., 1998). As much as 60% of MS lesions resolve over six

months while the remainder show evidence of persistent damage (Sahraian et al., 2010). In this stage, all subjects will receive baseline pCASL and DSC MRI and will then be randomized to first receive either daily oral therapy with either "**Treatment A**", extended-release ACZ capsules or "**Treatment B**", placebo capsules for 24 consecutive weeks and undergo repeat imaging at predetermined intervals. MRI scans and clinical evaluations will be obtained every 6 weeks with contrast-based scans repeated every 12 weeks. Contrast will be administered every 12 weeks to determine DSC measures of blood flow and whether new lesions have formed and determine how blood flow is altered with ACZ.

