At the end of week 24, patients initially randomized to Treatment B will take 1000 mg extendedrelease ACZ capsules. Similar imaging and clinical evaluations will be performed for the second 24week period. All subjects will discontinue drug at week 48 and obtain a follow-up clinical visit two weeks later. Based upon established pharmacokinetics, the half-life of drug is between 60-75 hours and one would expect insignificant levels within two weeks of discontinuation.

To maintain blinding, patients, evaluating clinicians and MRI analysts will not be informed of treatment assignment or sequence of scans.

We anticipate that sustained increases in regional cerebral perfusion over 6 months will result in improved tissue integrity as measured using diffusion tensor metrics and fewer MS lesions that evolve to persistent black holes.

HYPOTHESIS AND OBJECTIVES

Hypothesis

The underlying hypothesis of this proposal is that long-term therapy with ACZ will improve cerebral perfusion in subjects with MS and this improved perfusion will result in improved tissue integrity in a proportion of MS lesions. To test this hypothesis, subjects will be treated with ACZ, a currently FDA approved agent previously shown in healthy controls to increase cerebral perfusion (Sullivan et al., 1987; Vagal et al., 2009). Subjects will be scanned at various time points (see sections 4 and 6.3) and quantitative MRI metrics will be used to evaluate lesion evolution during and after discontinuation

of treatment.

Primary & Key Secondary Objective

Determine the degree to which divided daily doses of ACZ improves global and regional cerebral perfusion in subjects with MS.

Study subjects will obtain serial MRI scans prior to, during and after therapy (see sections 4 and 6.3). Cerebral blood flow will be measured using an optimized pCASL technique as described by Aslan (Aslan et al., 2010). This will allow us to test the first component of our hypothesis that treatment with ACZ will result in increased regional and/or global perfusion.

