	Day -7 Screen	Wk 0 Visit 1	Wk 2 Visit 2	Wk 4 Visit 3	Wk 6 Visit 4	Wk 8 Visit 6					
Treatment		500 mg PO BID	1000 mg PO BID	1500 mg PO BID	2000 mg PO BID						
H&P	Х	Х	Х	Х	Х	Х					
CBC, CMP	Х					Х					
Urine pregnancy*	Х										
pCASL MRI		Х	Х	Х	Х	Х					
MSFC		Х	Х	Х	Х	Х					
EDSS		Х	Х	Х	Х	Х					
Blood Sample X X X X X X											
* Female participants who have already been evaluated for pregnancy will not be retested unless otherwise indicated											

•												

Stage 2a – Safety/Tolerability & Kinetics of Treatment Effect										
Up to a Total of 10 subjects										
	Wk -4 Screen	Wk 0 Visit 1	Wk 6 Visit 2	Wk 12 Visit 3	Wk 14 Visit 4					
Treatment		1000 mg ACZ BID		d/c ACZ						
H&P	Х	X	Х	Х	Х					
CBC, CMP		X	Х	Х	Х					
Urine pregnancy*		X								
DSC MRI		X		Х						
pCASL MRI		X	X	x	X					
MSFC		X	Х	Х	Х					
EDSS		X	Х	Х	Х					
MFIS, MSWS-12		X	X	x	X					
Blood Sample		X	X	X	X					
* Female pa unless other	rticipants who wise indicated	have already been evaluated	for pregnancy	/ will not be r	retested					

- Additional CBC,CMP will be performed if measured ALT/AST > 1X ULN or if other alterations above baseline

- EDSS Expanded disability status scale
- MSFC Multiple Sclerosis Functional Composite Scale

Stage 2b – Tolerability & Tachyphylaxis of ACZ in MS Subjects									
• Up	to a Tota	I of 10 subjects		-					
	Wk -1 Screen	Wk 0 Visit 1	Wk 6 Visit 2	Wk 12 Visit 3	Wk 18 Visit 4	Wk 24 Visit 5			
Treatment		ACZ at dose identified in Stage 1b							
H&P	Х	X	X	Х	Х	Х			
CBC, CMP		Х	Х	Х	Х	Х			
Urine		Х							
pregnancy*									
DSC MRI		Х		Х		Х			
pCASL MRI		X	Х	X	x	Х			
MSFC		Х	Х	Х	Х	Х			
EDSS		Х	Х	Х	Х	Х			
MFIS, MSWS-12		X	Х	Х	х	Х			
Blood Sample		X	Х	Х	X	X			
* Female pa otherwise in	rticipants v dicated	who have already been evaluat	ed for pregna	ncy will not b	be retested u	nless			

- Additional CBC,CMP will be performed if measured ALT/AST > 1X ULN or if other alterations above baseline
- EDSS Expanded disability status scale
- MSFC Multiple Sclerosis Functional Composite Scale

Stage 3 – F	RCT; Lor	ng-term ther	apy wit	h ACZ	in MS S	Subject	S				
Del	layed-sta	rt design with	n oral th	erapy "	'Treatm	ent A"	(ACZ) o	or "Trea	tment l	B" (placebo)
 Tot 	al of 60 s	subjects									
	Wk -1 Screen	Wk 0 Visit 1	Wk 6 Visit 2	Wk 12 Visit 3	Wk 18 Visit 4	Wk 24 Visit 5	Wk 30 Visit 7	Wk 36 Visit 8	Wk 42 Visit 9	Wk 48 Visit 10	Wk 50 Visit 11
Treatment		Randomize to ACZ or placebo								d/c treatment	End Study
H&P	Х	Х	Х	Х	Х	Х	Х	Х	Х	Х	

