Stage 1b - Participants in this stage of the study will be given escalating divided doses of oral ACZ up to 4000 mg per day to determine both the magnitude of change to cerebral perfusion with maintenance daily oral ACZ therapy and to define the optimum dose(s) for additional studies. Stage 1b and 2 of the study will utilize extended release oral ACZ, distributed by Hermann Research pharmacy and self-administered by the subject.

r	500mg BID	1000 mg BID	1500 mg BID	2000 mg BID	_	Legend + MPL pCASI
W -1	w o	W 2	W 4	W 6	W 8	+ MSFC + EDSS
Screening	+	÷	+	+	+	
	±	‡	+ *	+ +	+ *	

Treatment and data collection for stage 1b will take 2.5 months for each enrolled subject. As many as two subjects can be evaluated during the month and we would anticipate that this portion of the study can be completed within twelve months.

Image analysis will be performed once each subject completes treatment. Cerebral perfusion measures will be determined for each dose by the same unblinded analyst (S.D.).

Stage 2a - This stage will continue to gather information about whether daily oral ACZ is tolerated and the kinetics of the treatment effect. Patients continue on the same dose for 12 consecutive weeks and undergo repeat imaging at predetermined intervals. Sustained treatment over a short duration will allow us to rapidly determine whether sustained treatment with ACZ can alter cerebral blood flow and will provide a go/no-go for future studies using this drug/paradigm. Patients will obtain MRI scans and clinical evaluations every 6 weeks with contrast-based scans repeated at 12 weeks.

Stage 2b - This stage will determine long-term tolerability and if tachyphylaxis is present with oral ACZ. Patients will continue on the same dose for 24 consecutive weeks and undergo repeat imaging at predetermined intervals. MRI scans and clinical evaluations will be obtained every 6

weeks with contrast-based scans repeated every 12 weeks.

Stage 3 - This stage is a prospective delayed-start design to evaluate the potential for ACZ to persistently enhance cerebral perfusion and impact the evolution of MS lesions. This pilot study is anticipated to lead to a larger randomized phase 3 clinical trial.

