In those unusual instances where adequate control is not obtained by the twice-a-day administration of acetazolamide extended-release capsules, the desired control may be established by means of acetazolamide (tablets or parenteral). Use tablets or parenteral in accordance with the more frequent dosage schedules recommended for these dosage forms, such as 250 mg every four hours, or an initial dose of 500 mg followed by 250 mg or 125 mg every four hours, depending on the case in question.

Acute Mountain Sickness:

Dosage is 500 mg to 1000 mg daily, in divided doses using tablets or extended-release capsules as appropriate. In circumstances of rapid ascent, such as in rescue or military operations, the higher dose level of 1000 mg is recommended. It is preferable to initiate dosing 24 to 48 hours before ascent and to continue for 48 hours while at high altitude, or longer as necessary to control symptoms.

HOW SUPPLIED

Acetazolamide Extended-Release Capsules, 500 mg are white to off-white pellets filled in empty hard gelatin capsules with orange opaque cap imprinted with "EP" in black ink and white opaque body imprinted with "107" in black ink and are supplied as follows:

Unit dose packages of 30 (3x10) NDC 68084-401-21

Storage and Drug Accountability

Acetazolamide tablets will be stored at room temperature (between 68°F to 77°F) as suggested by the manufacturer. Intravenous formulation of ACZ will be stored as lyophilized powder at the temperature specified above in the Hermann Research pharmacy. Lyophilized powder will be reconstituted prior to infusion by the pharmacy. All study medication will be stored at the Hermann Research pharmacy and dispensed as needed during study.

TREATMENT

Rationale for Selection of Dose

The ACZ challenge test, using 1000 mg IV ACZ, is a commonly utilized clinical tool in evaluating patients with chronic intracerebral occlusive disease and is a reliable predictor of critically reduced cerebral perfusion (Vagal et al., 2009). Oral doses as high as 4000 mg daily have been previously used in the NORDIC clinical trial (NORDIC Idiopathic Intracranial Hypertension Study Group Writing Committee et al., 2014).

Participants in this study will be treated with the highest tolerated dose of oral ACZ extended release capsules shown to exert the greatest effect on cerebral perfusion. This dose will also be utilized for an anticipated subsequent large phase 3 trial to determine clinical efficacy.

Study Drug Formulations

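### The oral acetazolamide dose is stated in conflicting ways for Stages 1b, 2a and 2b, and Treatment A has no complete dose statement in Stage 3

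*Combined protocol and SAP*

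**What the plan says.** **Stage 1b.** Rationale for Doses Selected says participants are "given escalating divided doses of oral ACZ up to 1500 mg per day". Rationale for Study Design and Summary of Study Design both put the top at 4000 mg per day. The Visit Schedule table has four two-week steps, starting at 500 mg BID and ending at 2000 mg BID. Study Visits and Procedures describes five, starting at 250 mg BID and ending at 2000 mg BID.

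**Stages 2a and 2b.** Rationale for Doses Selected names both stages and says "subjects will be treated with ACZ, as determined in stage 1b, for six consecutive months". The Stage 2a schedule table nevertheless prints 1000 mg BID. For Stage 2b, Rationale for Study Design says "Patients will continue on 1000 mg BID dose for 24 consecutive weeks and undergo repeat imaging at predetermined intervals", the schedule table says "ACZ at dose identified in Stage 1b", and Summary of Study Design says only "Patients will continue on the same dose for 24 consecutive weeks", with no figure.

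**Stage 3.** The one strength given is in Rationale for Study Design, for the second 24-week period: "patients initially randomized to Treatment B will take 1000 mg extendedrelease ACZ capsules". No frequency follows. For the arm that starts on ACZ, neither the schedule table nor the randomization text nor the visit text gives a strength or a frequency. Study Drug Formulations defines Treatment A by product and supplier. The Visit 5 text moves the placebo arm to Treatment A and keeps everyone on Treatment A to week 48.

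**Not tied to a stage.** Rationale for Selection of Dose, in the Treatment section, says "Participants in this study will be treated with the highest tolerated dose of oral ACZ extended release capsules", choosing the dose with the greatest perfusion effect.

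**The concern.** Within Stage 2b the dose is both set in advance and left to the result of another stage. Someone dispensing from the text and someone dispensing from the table could give different amounts. In Stage 3, the only randomized stage, the active treatment is a label with no complete dose behind it.

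Two things are at stake. The first is practical. Study Drug Administration has capsules dispensed in the quantity needed for each visit, and that quantity cannot be worked out without an amount per intake and a number of intakes per day. The same gap applies to the placebo count. The second is interpretation. Stage 2a is a go/no-go, and Stage 2b is there to show tolerability and tachyphylaxis. How far either supports Stage 3 depends on how their dose relates to the Stage 3 dose, and the protocol does not say. The week-24 comparison with placebo is the primary outcome, yet the dose whose effect it would estimate is not written down.

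**Working it through.** The plan has no stated figure to reproduce here. The check converts each dose statement to mg/day and sets the statements side by side.

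| Stage | Where | Dose as written | mg/day |
|---|---|---|---|
| 1b ceiling | Rationale for Doses Selected | 1500 mg per day | 1500 |
| 1b ceiling | Rationale for Study Design; Summary of Study Design | 4000 mg per day | 4000 |
| 1b steps | Visit Schedule | 500, 1000, 1500, 2000 mg BID | 1000, 2000, 3000, 4000 |
| 1b steps | Study Visits and Procedures | 250, 500, 1000, 1500, 2000 mg BID | 500, 1000, 2000, 3000, 4000 |
| 2a | Visit Schedule | 1000 mg BID | 2000 |
| 2a, 2b | Rationale for Doses Selected | set by Stage 1b | open |
| 2b | Rationale for Study Design | 1000 mg BID | 2000 |
| 2b | Visit Schedule | set by Stage 1b | open |
| 3, delayed start, weeks 24-48 | Rationale for Study Design | 1000 mg, no frequency | 1000 or 2000 |
| 3, early start | all Stage 3 text and schedule | none | not stated |
| any | Rationale for Selection of Dose | highest tolerated, greatest effect | depends on data |

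**Stage 2b.** The fixed dose is 1000 × 2 = 2000 mg/day. If the dose is left to Stage 1b, the schedule's steps allow 1000 to 4000 mg/day, which is 1000/2000 = 0.5 to 4000/2000 = 2 times the fixed dose. The visit text's steps allow 500 to 4000 mg/day, which is 0.25 to 2 times.

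**Can Stage 1b supply the answer?** That depends on which Stage 1b is meant. Under the 1500 mg/day ceiling it could not have tested 1000 mg BID, since 2000 > 1500. Under the 4000 mg/day ceiling it could: 1000 mg BID is the second of four steps in the schedule and the third of five in the visit text. The 1500 mg/day ceiling therefore does not by itself show that 2000 mg/day is out of range. It shows that the Stage 1b range is also contradictory.

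**Stage 3.** The oral product described in the protocol is a 500 mg capsule, so 1000 mg is not a capsule strength. It is an amount per intake or per day. As a daily total it is 1000 mg/day; as an amount taken twice daily it is 2000 mg/day, a ratio of 2. The highest-tolerated rule, applied to the top step of either list, would allow up to 4000 mg/day. Across these readings the range is 4000/1000 = 4-fold.

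**Dispensing.** Visits are six weeks apart, or 42 days. With 500 mg capsules, one interval needs 2 × 42 = 84 capsules at 1000 mg/day, 4 × 42 = 168 at 2000 mg/day and 8 × 42 = 336 at 4000 mg/day. The text does not say which count applies.

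**The case against.** The strongest defence is that Stage 1b did identify 1000 mg BID and the Stage 2b table cell was not updated. This is Version 6 of a staged protocol, the sample size section refers to preliminary data, and the Stage 2a table carries the same 1000 mg BID. On that reading the Stage 2b text and table agree. It is plausible, but no sentence gives the Stage 1b result, and the conflict over the Stage 1b range would remain.

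A second defence is that the objectives speak of divided daily doses, so a single daily intake of 1000 mg is unlikely. That is fair, but 1000 mg/day can itself be divided, so 1000 and 2000 mg/day both remain possible.

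A reader might also infer that the two Stage 3 arms receive different doses in weeks 24-48, so that dose is confounded with start time and the pooled 24-week analyses mix doses. The documents do not support this. The Visit 5 text puts all subjects on the same Treatment A, and no section gives the arms different doses. What stands is narrower: the shared label carries no strength or frequency, so equal dosing is implied but not documented. An asymmetry after week 24, even if there were one, would not affect the primary week-24 comparison with placebo.

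Finally, a reader might say that the Stage 3 dose is left to Stage 1b. No section says so directly. Rationale for Doses Selected names only Stages 2a and 2b, and the highest-tolerated rule does not mention Stage 1b. The link rests on the statement that Stage 1b will define the best dose or doses for further studies.

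**Conclusion.** The point holds as an internal inconsistency. Stage 2b has a fixed dose in one place and a deferred dose in two others. Stage 2a is fixed in the schedule but deferred in the dose rationale. Stage 1b has two ceilings, 1500 and 4000 mg/day, and two sets of steps. Treatment A in Stage 3 has no complete dose statement.

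The ambiguity is 2-fold for the one Stage 3 figure (1000 or 2000 mg/day) and up to 4-fold if the highest-tolerated rule is applied to the listed Stage 1b steps. For Stage 2b, the deferred dose could lie between 0.5 and 2 times the fixed dose on the schedule's steps, or 0.25 and 2 times on the visit text's. These sizes assume that the Stage 1b steps are as printed and that the oral product is the 500 mg capsule described. They show what the wording permits and do not show that any participant received a different dose. The conclusion depends on no power or sample-size figure.

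**What to change.** Reconcile the following so that each stage has one dose statement that nothing else contradicts:

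- Rationale for Doses Selected
- the Stage 1b, 2b and 3 paragraphs of Rationale for Study Design
- the Stage 1b, 2a and 2b schedule tables
- the Stage 1b and 2b paragraphs of Summary of Study Design
- the Stage 1b visit text and the Stage 3 Visit 5 text
- Rationale for Selection of Dose
- Study Drug Formulations

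Define Treatment A once, with strength and frequency, and have every stage that uses it cite that definition. State how it relates to the Stage 1b result. If Stage 1b is complete, report what it identified; if it does not set later doses, say so. Give the Stage 1b ceiling and steps once. Which dose or rule applies is for the sponsor to settle.

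The cost is a wording amendment and a matching pharmacy order, with no added patients, visits or procedures.

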The primary endpoint of this study will be to determine if therapy with oral divided-dose ACZ administered each day for week-long period results in at least 15% increase in CBF. Studies have shown between 10% - 15% decrease in cerebral perfusion in patients with relapsing MS (Adhya et al., 2006). Therefore, increases in CBF of at least 15% might result in change to lesion evolution. Baseline CBF measures will be compared to measures obtained at each dose escalation step using paired *t* test and Mann-Whitney test.

Determine the effect of long-term oral ACZ on lesion evolution. The key secondary endpoint of this study is to determine if long-term use of oral daily divided-dose with ACZ improves tissue integrity in a proportion of MS lesions.

MRI scans will be segmented using into white and gray matter, T2 and T1 lesion components and contrast-enhancing lesion component. Expert raters (I.V., S.D., L.F.), who are blinded to treatment arm (see section 6.1) will perform quality control of the automated segmentation and obtain quantitative measures of cerebral perfusion. The number and volume of T2 hyperintense and T1 hypointense lesion will be determined using MRIAP. The ratio of T1 hypointense/T2 hyperintense lesion will be determined for baseline and each crossover period and correlated with CBF, CBV and MTT measures obtained at similar times using the Spearman rank correlation.

Diffusion tensor imaging (DTI) is a reliable, validated technique that quantitatively measures molecular diffusivity within tissue and provides information about its microstructural integrity. DTI will be used to monitor tissue integrity and correlate change with increases in CBF following ACZ.

Tertiary Objectives

Several studies have quantitated transverse and longitudinal relaxation times within lesions and normal-appearing white matter and gray matter. These studies have shown that changes in both transverse and longitudinal relaxation can precede lesion formation and possibly better evaluate lesion evolution as compared to black hole volumes (Papadopoulos et al., 2010; van Walderveen et al., 1999a; Walsh et al., 2014; Warntjes et al., 2013). We will manually delineate regions of interest within lesions to obtain T2 and T1 relaxometry metrics. Lesions within areas with greatest change in CBF will be compared with those with least change. We anticipate a correlation between relaxometry measures and areas with varying CBF.

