During the dose escalation, in addition to issues of tolerability, subjects will be monitored at each transition point for the following specific serious AEs: paraesthesia, change in taste, accelerated change in blood pressure or fluid retention. Any subject with serious AEs will be withdrawn from the study. Patients with persistent serious AEs will be treated using standard medical practice.

STUDY POPULATION

List the number of subjects to be enrolled.

This exploratory study is designed to evaluate the long-term effects of oral ACZ on CBF in adult subjects with MS. We will enroll 100 MS subjects between the age of 18 and 55 without history of cerebrovascular disease or glaucoma.

There are several studies suggesting that MS lesions in the pediatric population differ from that typically seen in the adult population (Ghassemi et al., 2014; Renoux et al., 2007). To minimize potential confounding variables, all stages of the study will recruit only adult subjects with MS.

All subjects will be recruited from patients seen at the MS clinic located at the University of Texas Professional building (UTP) Neurology practice

Information about the study will be available on the UT Neurology web site and in print format at the UTP MS clinic.

Informed consent will be obtained from each participant prior to entry and, for subjects who elect to

participate in multiple parts of the study, prior to each stage.

Criteria for Recruitment

Subjects who wish to participate in either stage of the study will be evaluated by the principle investigator to determine if they meet inclusion and exclusion criteria. A thorough medical history will be performed to determine if any pre-existing cardiovascular disease or glaucoma is present. Subjects whose history is unknown will be encouraged to obtain evaluation by a primary care physician and eye-care specialist prior to recruitment. In addition, available blood tests, performed within six months of study entry, will be reviewed to determine if any renal or hepatic dysfunction is present.

Potential subjects with historical or laboratory evidence to suggest dysfunction in one of the above clinical systems will be excluded from study participation. As the rate of these comorbidities is low in a young population, we do not anticipate large numbers of failures at this stage of screening.

Inclusion Criteria

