The primary aim of the proposed study is to evaluate the change in global CBF with ACZ, so the primary outcome is the change in global CBF after 24 weeks relative to pre-treatment baseline. Based on the preliminary data, we expect to see a 15% difference between the ACZ treatment and placebo groups on the improvement in global cerebral perfusion with standard deviation (SD) of 30%. We ran Monte Carlo simulations under a linear mixed effect model (same model as planned for analysis) and calculated a needed total sample size of n=50 to detect a group difference of 0.5 SD at the 24 weeks (phase 1) assuming a within-subject correlation of 0.5, a significance level of 0.05, and 90% power. We hypothesize a similar group difference in phase 2 (ACZ-ACZ group would not change between weeks 24 and 48 but delayed-start group would improve) and similar power to detect this effect. With 50 patients, for Aim 1.2, we will have 80% power to detect an average correlation as low as 0.39 between CBF and MD or FA. Considering a dropout rate of 18%, we need to recruit 60 participants. Aims 2 are mainly exploratory and parameters derived from this study will be used to help design future larger scale confirmatory studies.

All analyses will be intent-to-treat. To summarize the data, descriptive statistics will be used. Demographics and baseline characteristics at randomization will be summarized for each treatment arm. Generalized linear mixed models will be used to analyze all outcomes and will include treatment group and time, group-by-time interaction, and disease duration (stratifying variable) as covariates, and a random intercept to account for within-patient correlation.

For the primary outcome, we will focus on comparing the treatment groups in phase 1. A linear mixed model will be used to compare the estimated change in global CBF between baseline and week 24 in the ACZ and delayed-start groups. A secondary analysis will study ACZ treatment effect on CBF in different regions by treating regions as clusters in the linear mixed model. If normality of CBF outcome does not hold, an appropriate transformation or different outcome distribution will be used.

For the secondary endpoint at 48 weeks (phase 2), a similar mixed model will be used to compare changes in global CBF between weeks 24 and 48 weeks in the early-start and delayed-start groups. The model will include the same terms as for phase 1.

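### Section 2.2 makes an open-label dose-step CBF rise the study's primary endpoint, while Section 11 names and sizes the randomised 24-week change in global CBF

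*Combined protocol and SAP*

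**What the plan says.** Section 2.2 (Primary & Key Secondary Objective): "The primary endpoint of this study will be to determine if therapy with oral divided-dose ACZ administered each day for week-long period results in" a CBF increase of at least 15%. The analysis follows: "Baseline CBF measures will be compared to measures obtained at each dose escalation step using paired" *t* "test and Mann-Whitney test". The paragraph does not say whether CBF is global or regional. The hypothesis just before it is that "treatment with ACZ will result in increased regional and/or global perfusion".

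Section 11 (Sample Size and Statistical Methods): "the primary outcome is the change in global CBF after 24 weeks relative to pre-treatment baseline". It adds: "For the primary outcome, we will focus on comparing the treatment groups in phase 1". The model is a linear mixed model comparing the ACZ and delayed-start groups from baseline to week 24. The sizing statement is that the authors "calculated a needed total sample size of n=50 to detect a group difference of 0.5 SD at the 24 weeks", with 60 recruited.

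Section 3 (Study Population) describes the aim this way: "This exploratory study is designed to evaluate the long-term effects of oral ACZ on CBF in adult subjects with MS".

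The Trial Schedule (Section 4) puts dose escalation in Stage 1b, with up to 10 subjects. Section 5 has Stage 1b CBF measured by an unblinded analyst. The Blinding paragraph of Section 8 makes Stage 3 the only double-blind stage.

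**The concern.** A study can have only one outcome that decides its primary result, unless the plan says how several are combined. Here two definitions claim that position. They differ in stage, duration, comparator, brain region, success criterion and test. One rests on an uncontrolled, unblinded before-and-after comparison in a handful of subjects; the other on a blinded randomised comparison. If the two disagree, the plan does not say which result is the study's.

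The Section 2.2 version also has no decision rule. A test of change against zero does not show that the rise is at least 15%, and nothing says whether one dose step, a particular step or all steps must meet the mark.

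A smaller defect sits beside it. Mann-Whitney is a test for independent groups, but the Stage 1b scans are repeat scans of the same people.

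**Working it through.** **1. The two definitions side by side**

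| Attribute | Section 2.2 | Section 11 |
|---|---|---|
| Stage | Not named; dose steps exist only in Stage 1b | Placebo groups exist only in Stage 3 |
| Duration | One week | 24 weeks |
| Comparator | Own baseline | Randomised group |
| Region | Not stated | Global |
| Criterion | Rise of at least 15% | Group difference |
| Test | Paired t, Mann-Whitney | Linear mixed model |
| Sample size | None | 50 evaluable, 60 recruited |

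Stage 1b is an inference, because Section 2.2 names no stage. It is a firm one, because no other stage has dose steps. The one-week duration does not match Stage 1b either: Sections 4 and 6.3 give two-week steps. The number of steps differs too, with four in Sections 4 and 5 and five in Section 6.3.

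**2. The plan's own figure**

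The effect is 15/30 = 0.5 SD. Dropout gives 50/(1 − 0.18) = 60.98, so 61 against the 60 stated, and 60 is the Stage 3 total in Section 4. The sizing therefore belongs to Stage 3 alone.

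The 50 itself does not follow from a simple two-sided comparison of change with SD 30%. That needs 2(1.960 + 1.282)²/0.5² = 84.1, or 85 per arm (170 in total), and 25 per arm gives Φ(0.5/√(2/25) − 1.960) = 42% power. The simulation settings are not given. This is a separate question and nothing below depends on it.

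**3. What the Section 2.2 rule could produce**

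Assumptions, none of them in the plan:
- n = 10, paired t test at two-sided 0.05 at each step
- any step counts as success
- all steps share one baseline, with correlation 0.5 between visits
- SD of change from 10% to 30% (the documents give no Stage 1b SD; 30% is the Section 11 value)

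Success at a step means t > t₉(0.975) and, where stated, an observed mean of at least 15%. The probability p was found by simulation. The chance that either primary shows a false increase is 1 − 0.975 × (1 − p), treating the stages as independent. For the Section 11 outcome alone it is 2.5%.

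| SD of change | p, no effect (four / five steps) | Either primary falsely increased | True rise 10%: significant with observed mean of at least 15% |
|---|---|---|---|
| 10% | 0.0 / 0.0% | 2.5 / 2.5% | 16 / 19% |
| 15% | 0.3 / 0.3% | 2.8 / 2.8% | 35 / 39% |
| 20% | 2.4 / 2.9% | 4.9 / 5.4% | 42 / 46% |
| 30% | 6.8 / 8.2% | 9.2 / 10.5% | 36 / 40% |

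The third column uses unrounded p; for example, 1 − 0.975 × (1 − 0.0684) = 9.2%. Without the 15% requirement, p is 8.1% for four steps and 9.5% for five at any SD. Results barely change at correlation 0.3 or 0.8.

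The last column uses a true rise below the 15% mark, so it shows how often the mark would appear to be met when it is not. The 95% confidence interval half-width, t₉(0.975) × SD/√10, is 7.2, 10.7, 14.3 and 21.5 points at SD 10, 15, 20 and 30%.

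**4. Mann-Whitney on paired scans**

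Exact tests, n = 10, shift of 0.5 SD of change, correlation assumed:

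| Correlation | Mann-Whitney power | Signed-rank power | Mann-Whitney rejection with no effect |
|---|---|---|---|
| 0.3 | 18% | 28% | 2.0% |
| 0.5 | 10% | 28% | 0.9% |
| 0.7 | 3.6% | 28% | 0.2% |
| 0.9 | 0.2% | 28% | <0.1% |

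The error is conservative: it loses power and does not create false positives.

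**The case against.** The best reply is that a careful reader can tell which outcome ranks first. Section 11 ties its outcome to the primary aim of the study and gives timepoint, contrast, model and sample size. Section 2.2 gives no size and no rule. Section 5 calls the early stages proof of principle, and Stage 1b is there to find a dose. Section 2.2 also still refers to crossover periods although Stage 3 is described as delayed-start, which suggests leftover wording more than a deliberate second primary. This stands as evidence of intent, but no sentence limits the Section 2.2 endpoint to one stage or says that Section 11 replaces it.

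Section 11 also assigns mixed models to all outcomes, which could be read as displacing the paired tests. But that model contains a treatment-group term, and Stage 1b has no groups to compare.

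The objection to the arithmetic carries weight. The rule that any step counts is assumed. With one prespecified step and the same 15% requirement, false success is 2.1% at SD 30%, 0.7% at 20% and 0.1% at 15%, all below 2.5%. The results for a true 10% rise are not false findings of an increase; they show overestimation in a small sample judged against a threshold. So the figures illustrate the risk and do not carry the finding.

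It is also fair that Mann-Whitney and the schedule conflicts are lesser, separate defects. They are noted because they sit in, or bear directly on, the paragraph that has to be rewritten.

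**Conclusion.** The concern holds. Two incompatible definitions are each worded as the primary of the whole study, and the plan does not rank them. This follows from the text and needs no assumption beyond linking dose-escalation steps to Stage 1b.

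The numerical size is uncertain. If any step may count, the chance that at least one primary shows a false increase is 9.2 to 10.5% at SD 30%, 4.9 to 5.4% at 20% and 2.8% at 15%, against 2.5% for the Section 11 outcome alone. These depend on the assumed SD, n = 10 and independence between stages. They do not include any bias from the open-label, unblinded assessment.

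This should be fixed but is not fatal, because Section 11 already specifies which randomised comparison should serve as the primary. The Mann-Whitney error is minor, since a valid paired t test is named beside it.

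**What to change.** 1. In Section 2.2, name the Section 11 outcome as the study's primary endpoint: the Stage 3 ACZ-placebo difference in change in global CBF from baseline to week 24. Label the dose-step comparison as a Stage 1b objective, exploratory or as an endpoint of that stage only, that cannot by itself establish the study's primary result. State whether it uses global or regional CBF.
2. Replace Mann-Whitney with the Wilcoxon signed-rank test.
3. Report each Stage 1b mean change with its 95% confidence interval against the 15% mark. Do not read p < 0.05 against zero as showing a rise of at least 15%.
4. The sponsor should reconcile the passages on dosing duration (Section 2.2 against Sections 4 and 6.3) and on the number of dose steps (Sections 4 and 5 against Section 6.3).

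The cost is protocol and SAP wording only; no new data are needed.
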